	

 Time spent in defined glucose ranges Average daily glucose BG variability parameters (e.g., coefficient of variation as percentage of mean level [% CV], etc.) Low blood glucose index (LBGI) High blood glucose index (HBGI)
• Change from baseline in Homeostasis Model Assessment of Insulin Resistance (HOMA-IR)• Change from baseline in Homeostatic Model Assessment of Insulin Secretion (HOMA-B)• Change from baseline in fasting plasma glucose (FPG)
Exploratory/ Other Objectives and Endpoints	To evaluate the effect of hepatic ultrasound insonification on glucose metabolism parameters, assessed by: 
• Change from baseline in exploratory biomarkers (blood samples will be stored for potential later analysis), e.g., but not limited to:
 Glucagon Glucagon-like peptide 1 (GLP-1), total Leptin Ghrelin• Change from baseline in long-term glucose parameters
 Hemoglobin A1c (HbA1c) Fructosamine• Change from baseline in lipid metabolism parameters
 Free fatty acids (FFAs) Triglycerides (TG) Total cholesterol Low-density lipoprotein (LDL-C) High-density lipoprotein (HDL-C) Very low-density lipoprotein (VLDL-C)• Change from baseline in inflammatory biomarkers (blood samples will be stored for potential later analysis), e.g., but not limited to:
 Cytokines (IL-6) Adiponectin C-reactive protein (CRP)
Phase of Development	1
Number of Study Sites	1
Study Population	Subjects with T2DM

Number of Subjects	Approximately 15 subjects will participate in this study. Drop-outs may be replaced in order to achieve 15 completed subjects.

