Summary of Study Design	
This is an open label, exploratory pilot study to assess the effects of hepatic ultrasound insonification on glucometabolic parameters in subjects with T2DM through selective hepatic ultrasound of the porta hepatis region of the liver utilizing pulsed ultrasound.
 
Assessments will be performed via CGMs, OGTT, HE-clamp with stable isotope labeled glucose ($[6,6-^2\text{H}_2]$ glucose), measurements of insulin secretion and resistance (e.g. HOMA-IR), change in glucose parameters, inflammatory biomarkers and potential analysis of exploratory biomarkers.
 
The study will be conducted in 1 cohort, enrolling approximately 15 subjects.
 
Subjects will undergo a Screening Period of up to 28 days, an approximately two week (Days -1 to 14) Observational Period, follow by three consecutive days of ultrasound Insonification (Days 15, 16 and 17) and a second Observation Period of 11 additional days (Days 18 to 28).
 
Screening:
 
A Screening Visit will be performed up to 28 days prior to the first in-house period to identify eligible subjects for the study. For eligible subjects with a $\text{BMI} > 35.0$ and $\leq 40.0 \text{ kg/m}^2$ and/or a waist circumference > 40 and ≤ 45 inches, an ultrasound examination will be added to confirm eligibility, and the screening period will be extended for at least 30 days for these subjects.
 
In-house Period 1:
 
Day -1: Subjects will check in to the clinic in the morning on Day -1 for a 3-day in-house period. A urine pregnancy test (if applicable), and urine drug screen and alcohol breath test will be collected.
 
Subjects get instructions on maintaining their regular diet and physical activity.
 
Subjects will receive standardized meals throughout their in-house stay. Food intake will be recorded during the entire in-house period by study staff.
 
Subjects will be connected to a CGM (e.g., Dexcom G6) for the entire study period. Subjects will be blinded to the CGMS data. Continuous glucose monitoring data from Day -1 to Day 14 will be used for the baseline assessment. Subjects will be provided with a glucometer. They will be instructed on how to use the glucometer and to monitor their fasting plasma glucose levels daily during the outpatient periods. They will be instructed to contact the study staff, if FPG $> 220 \text{ mg/dL}$, they experience symptoms of hypoglycemia, or measures an FPG $< 70 \text{ mg/dL}$. Subjects will be frequently contacted by qualified study site staff to review their fasting plasma glucose values.
 
Blood samples will be taken for safety assessments.
 
Subjects will be instructed to fast overnight.

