HOMA-B

Fasting Insulin

Fasting C-Peptide

Incretins/exploratory

biomarkers:

Total GLP-1
Glucagon
Leptin
Ghrelin

Inflammatory biomarker:

Cytokines (IL-6)
Adiponectin
CRP

- (a) Assess only if total bilirubin ≥ 2.0 mg/dL.
- (b) Microscopic analysis should be performed only if urine evaluations are abnormal.
- (c) In the event of abnormal TSH, Free T3/T4 may be collected at Principal Investigator discretion.

The responsible laboratories will perform all assigned laboratory tests, e.g., listed above. Specialty labs may be responsible for specific laboratory parameters. The results of laboratory tests will be sent to the Principal Investigator or designee, who is responsible for reviewing these results. All laboratory safety data will be faxed or transferred electronically.

Laboratory reports must be signed and dated by the Principal Investigator or designee indicating that the report has been reviewed and any abnormalities have been assessed for clinical significance.

All clinically significant laboratory abnormalities must be recorded as an ADE. A clinically significant laboratory abnormality may be verified by retesting and may be followed upon discretion of the Principal Investigator.

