9.1.19 Oral Glucose Tolerance Test (OGTT)

An oral glucose tolerance test (OGTT) will be administered at the time points specified in the [Schedule of Events \(SOE\)](#).

Subjects will be fasted \geq 10 hours prior to the OGTT. At approximately 08:00 h-09:00 h the OGTT will begin. Subjects will be asked to drink 75 g of glucose in a 10-fluid ounce beverage over 5 minutes. The glucose ingestion will be followed by approximately 100 mL of water. The subject will rest for the duration of test and will abstain from eating. Only small amounts of water may be consumed for the duration of the test. Sampling for fasting glucose, C-peptide, insulin sampling will be performed before the OGTT and 15, 30, 60, 90, 120, 150 and 180 min after the start of the glucose administration.

The time of all blood draws and the time when the subjects start to drink the glucose solution will be recorded.

OGTT sampling schedule: Time points are relative to start of OGTT procedure. All samples will be taken within a window of \pm 3-minutes.

All OGTT procedures during the in-house periods on Day 1 and Day 16 will follow the same schedule.

The OGTT procedure for each subject (inter-individual) will start one hour (nominal time) after the start of their hepatic ultrasound insonification. A window of \pm 15 minutes will be allowed.

Insonification and OGTT on Days 1 and 16 should start at the same time (actual time) for each subject (intra-individual).

Table 9-2 Sampling Schedule for OGTT

Nominal time (min) relative to Start of OGTT	-15	0	15	30	60	90	120	150	180
Standard Test Solution (75 g dextrose)		X							
Plasma Glucose	X		X	X	X	X	X	X	X
Insulin and C-peptide	X		X	X	X	X	X	X	X

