5.4. Baseline, Post-Baseline Changes, and Last Observed Value (LOV)

Unless stated otherwise, baseline and post-baseline change values will be based on the following:

Baseline will be based on the last non-missing value collected prior to the first on study HUI. Post-baseline values will be those collected after initiation of the first HUI.

Change from baseline is defined as: value – baseline value.

Percent change from baseline is defined as: $[(\text{value} - \text{baseline value})/\text{baseline value}] \times 100\%$.

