In addition to the continuous summary, the overall interpretation of ECG results will be summarized as within normal limits, abnormal without clinical significance, and abnormal with clinical significance by visit and time point.

All ECG data will be listed.

Whole-body insulin sensitivity

The effect of hepatic ultrasound insonification on changes from baseline in whole-body insulin sensitivity during a two-step HE Clamp will be assessed by:

- Insulin Sensitivity Index (SI)
- Glucose disposal rate during steady state (M)
- Glucose metabolic clearance rate during steady state (MCR)

The formulas for SI, M, and MCR are described in section 6.8. Each parameter will be summarized using descriptive statistics in the Ultrasound Insonification Effect Population.

Glucose tolerance and insulin secretion

To evaluate the effect of hepatic ultrasound insonification on change from baseline in glucose tolerance and insulin secretion, assessed by an oral glucose tolerance test (OGTT), area under the curve (AUC) total and incremental time (e.g., $AUC_{0-180\text{min}}$) will be calculated.

AUC is calculated according to the linear trapezoidal rule:

$$\frac{AUC(t_i)}{t_{i+1}} = \frac{C_i + C_{i+1}}{2} \times (t_{i+1} - t_i)$$

where C is glucose concentration (mg/dL) with measurements at times $t_1..t_n$ such that

$$AUC_{\text{total}} = \sum_{i=1}^{n-1} AUC(t_i)$$

$AUC_{0-180\text{min}}$ is similarly derived but uses data only through 180 minutes.

AUC results will be summarized using descriptive statistics in the Ultrasound Insonification Effect Population.

Glucose metabolism parameters

The effect of hepatic ultrasound insonification on glucose metabolism parameters will be evaluated by the following endpoints in the Ultrasound Insonification Effect Population:

- Blood glucose (BG) profiles assessed with continuous glucose monitoring system (CGMS)
 - Time spent in defined glucose ranges
 - Average daily glucose
 - BG variability parameters (e.g., coefficient of variation as percentage of mean level [% CV], etc.)
 - Low blood glucose index (LBGI)
 - High blood glucose index (HBGI)
- Homeostasis Model Assessment of Insulin Resistance (HOMA2-IR)
- Homeostatic Model Assessment of Insulin Secretion (HOMA2-B)
- Fasting plasma glucose (FPG)

The baseline period for CGMS parameters will be calculated using data starting from 14:00h on Day -1 to 22:00h on Day 1, omitting data collected between a subjects OGTT glucose consumption start time + 180 minutes.

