The primary insonification analysis period for CGMS parameters will be from 14:00h on Day 15 to 22:00h on Day 16, omitting data collected between a subjects OGTT glucose consumption start time + 180 minutes.

The CGMS parameters will be summarized in a table using descriptive statistics for the primary insonification analysis period and change from baseline. The CGMS parameters for the baseline period, primary insonification analysis period and Days 19 and 20 will be listed.

The percent of time spent in defined glucose ranges will be calculated separately for each of the analysis periods along with the change from the baseline period. The following glucose ranges will be defined and presented separately:

- > 250 mg/dL (>13.9 mmol/L)
- > 180 mg/dL (>10.0 mmol/L)
- 70-180 mg/dL (3.9-10.0 mmol/L)
- < 70 mg/dL (<3.9 mmol/L)
- < 54 mg/dL (<3.0 mmol/L)

Average daily glucose will be calculated based on the applicable glucose measurements obtained during the specified day/period.

To calculate the LBGI and HBGI, the original BG data for each day/period is transformed such that it is centered by zero and bound between $-\sqrt{10}$ and $\sqrt{10}$.

$$f(BG, \alpha, \beta) = [(\ln(BG))^{1.084} - 5.381] * 1.509$$

The transformed values are then inputted into the BG risk function:

$$r(BG) = 10 * f(BG, \alpha, \beta)^2$$

The risk of each observation is further transformed into two series, risk of low BG series, $rl(BG)$, and risk of high BG series, $rh(BG)$:

$$rl(BG) = r(BG) \text{ if } f(BG) < 0 \text{ and } 0 \text{ otherwise}$$

$$rh(BG) = r(BG) \text{ if } f(BG) > 0 \text{ and } 0 \text{ otherwise}$$

These series are then averaged to produce the LBGI and the HBGI as follows:

$$LBGI = \frac{1}{n} \sum_{i=1}^n rl(x_i)$$

$$HBGI = \frac{1}{n} \sum_{i=1}^n rh(x_i)$$

Absolute values and changes from baseline will be summarized using descriptive statistics for BG, HOMA2-IR, HOMA2-B, and FPG. Baseline is defined as the last non-missing value collected prior to a subject's first HUI. The HOMA2 results will be produced by the HOMA2 calculator with fasting plasma glucose and insulin concentration obtained from safety laboratory

assessments as the inputs. Summaries will be provided by study visit/time point as applicable in the protocol Schedule of Events.

For BG, coefficient of variation (CV) calculated as $100 \times [\text{standard deviation (SD)} \div \text{mean}]$ will be included with the other summary statistics.

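### HOMA2-B, the endpoint named as insulin secretion, is computed from fasting insulin alone although C-peptide is on the laboratory list, so it cannot separate secretion from hepatic insulin clearance

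*Protocol*

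**What the plan says.** The secondary endpoints in the Protocol (Study Summary and section 5.2) include "Change from baseline in Homeostatic Model Assessment of Insulin Secretion (HOMA-B"), next to HOMA-IR and fasting plasma glucose. The protocol does not give the inputs.

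SAP 6.9, under glucose metabolism parameters, does: "The HOMA2 results will be produced by the HOMA2 calculator with fasting plasma glucose and insulin concentration obtained from safety laboratory" assessments. One input pair serves both HOMA2-IR and HOMA2-B.

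C-peptide appears in the protocol in two places:

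- Table 9-1 (section 9.1.8) lists "Fasting C-Peptide" in the same block as fasting insulin, HOMA-IR and HOMA-B.
- Section 9.1.19 states "Sampling for fasting glucose, C-peptide, insulin sampling will be performed before the OGTT" and at seven later times, on Days 1 and 16.

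The SAP does not mention C-peptide. Its OGTT paragraph is headed as covering both glucose tolerance and insulin secretion, but the AUC formula is defined for one analyte: "where C is glucose concentration (mg/dL) with measurements at times". No insulin AUC, C-peptide AUC or insulin-clearance measure is specified. Insulin-based HOMA2-B is therefore the only measure of secretion for which the SAP gives a calculation.

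**The concern.** At fasting steady state, peripheral insulin is secretion divided by clearance. An index built on fasting insulin reads a fall in clearance as a rise in secretion, and a rise in clearance as a fall. The liver is a major site of insulin clearance. C-peptide is released with insulin and largely escapes hepatic extraction. Both statements are general physiology, not text from the documents.

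In many trials insulin-based HOMA is an acceptable approximation. It deserves a second look here because the intervention is "selective hepatic ultrasound of the porta hepatis region of the liver utilizing pulsed ultrasound", so the quantity that could confound the index belongs to the organ being treated. A pilot of this kind is meant to suggest a mechanism. If HOMA2-B moved, the planned summaries would leave two quite different explanations open, although the analyte that could help separate them is already on the laboratory list.

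**Working it through.** The documents contain no HOMA value, HOMA2 equation or clearance figure, so there is nothing to reproduce. The check has two parts.

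**1. How far the index moves if only clearance changes**

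Assumptions, none of them from the documents:

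- fasting insulin I = S / CL (S secretion, CL clearance);
- S and fasting glucose G unchanged;
- HOMA-B proportional to I. The closed forms HOMA-B = 20·I/(G − 3.5) and HOMA-IR = I·G/22.5 (I in µU/mL, G in mmol/L) stand in for the HOMA2 calculator;
- C-peptide clearance unchanged.

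If CL is multiplied by (1 + x), then I, HOMA-B and HOMA-IR are all multiplied by 1/(1 + x). C-peptide does not change, so the C-peptide:insulin ratio is multiplied by (1 + x).

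| Scenario | Insulin-based HOMA-B | Insulin-based HOMA-IR | Secretion read from C-peptide | C-peptide:insulin ratio |
|---|---|---|---|---|
| CL −20% | 1/0.8 = +25.0% | +25.0% | 0% | −20% |
| CL −10% | 1/0.9 = +11.1% | +11.1% | 0% | −10% |
| CL +10% | 1/1.1 = −9.1% | −9.1% | 0% | +10% |
| CL +20% | 1/1.2 = −16.7% | −16.7% | 0% | +20% |
| S +25%, CL unchanged | +25.0% | +25.0% | +25% | 0% |

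Worked example at G = 8.5, I = 15: HOMA-B = 20 × 15/5.0 = 60. With CL −20%, I = 15/0.8 = 18.75 and HOMA-B = 20 × 18.75/5.0 = 75, which is +25%. If glucose also fell by 0.25 or 0.5 mmol/L, HOMA-B would be 20 × 18.75/4.75 = 78.9 (+31.6%) or 20 × 18.75/4.5 = 83.3 (+38.9%).

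The first and last rows show the issue. Insulin-based HOMA-B is +25% in both, and only the C-peptide columns tell them apart.

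**2. Whether C-peptide is available where HOMA is read**

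- Both Schedules of Events have a HOMA-IR row on Days 1, 15, 18 and 28. Neither has a row for HOMA-B or fasting C-peptide.
- A general glucose-parameters row, with fructosamine as its example, falls on the same four days. Table 9-1 puts fructosamine and C-peptide in one block, so that row may cover C-peptide, but it does not say so.
- SAP 5.4 sets the baseline: "Baseline will be based on the last non-missing value collected prior to the first on study HUI". For HOMA this is the fasting sample on Day 15 before insonification, if not missing, so change from baseline is read at Days 18 and 28.
- C-peptide is explicitly timed only at the OGTTs on Days 1 and 16. Those samples cannot stand in for Days 18 and 28. They do give one before-and-after pair, with glucose, insulin and C-peptide taken at the same −15 minute draw (Table 9-2), since Day 16 follows the first two insonifications.

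**The case against.** The strongest reply is that the bias depends on an effect nobody has claimed. No passage says insonification alters insulin clearance; the protocol's targets are glucose utilisation, glucose tolerance, insulin sensitivity and glucoregulation. The percentages are an identity evaluated at assumed values and say nothing about what will happen. This stands, so the figures can serve only as illustration.

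Nor is the study blind to clearance. Protocol 9.1.22 calls for the same Step 1 insulin rate on Day 17 as on Day 2 and for a common Step 2 rate, with insulin sampled in each steady-state window. Insulin levels at matched infusion rates carry some information on clearance. This also stands, with limits: the SAP derives no clearance measure from them, the protocol lets the investigator adjust rates, and clearance under infused insulin is not fasting hepatic extraction.

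Insulin-based HOMA is also conventional, the study is exploratory and descriptive, and SAP section 5 lists all database data by subject, so recorded C-peptide would stay available. These points limit the importance of the problem. They do not give the reader of the summary tables a way to tell secretion from clearance.

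A reader might infer three stronger things that the documents do not support:

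- **The missing control arm makes this worse.** It does not. A treatment effect on clearance would move insulin-based HOMA2-B in a controlled trial as well.
- **Only HOMA2-B is exposed.** Insulin-based HOMA2-IR shifts by the same proportion in the illustration.
- **The repair certainly needs no extra laboratory work.** The schedule does not establish that C-peptide is assayed on Days 18 and 28.

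**Conclusion.** The point holds as a limit on interpretation with an inexpensive remedy. The only secretion measure that the SAP defines cannot separate insulin secretion from hepatic insulin clearance, in a trial whose treatment is aimed at the liver, and the SAP leaves unused an analyte that could help separate them.

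The size is unknown. Under constant secretion and glucose and an index proportional to insulin, a 20% clearance change in either direction reads as +25% or −16.7%. This rests on the assumptions listed in the working, including general physiology that the documents do not state.

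It would go too far to call the endpoint invalid, or to predict that a false change in beta-cell function will be reported. The documents give no evidence that clearance changes, and the SAP summarises HOMA2-B descriptively under its own name. The primary endpoints M/I, EGP and Rd do not use HOMA and are unaffected.

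**What to change.** In SAP 6.9:

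1. Compute HOMA2-B from fasting glucose and fasting C-peptide at every visit where fasting C-peptide is assayed, and keep the insulin-based HOMA2-B beside it.
2. Summarise the fasting C-peptide:insulin ratio by visit with its change from baseline, and read HOMA2-IR together with it. Include the Day 1 and Day 16 pre-OGTT samples, the one pair whose timing is explicit.
3. Where C-peptide is missing, state that HOMA2-B at that visit cannot separate secretion from clearance.

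Before finalising, confirm that C-peptide is assayed on the existing fasting samples at the HOMA visits (Days 1, 15, 18 and 28), and that the HOMA2 calculator version in use accepts C-peptide. The documents settle neither.

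The cost is SAP wording, a second calculator run, one more summary table and possibly an added assay on fasting draws already planned.

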3.0 LIST OF ABBREVIATIONS

Abbreviation	Definition
ADE	Adverse device effect
ALT	Alanine aminotransferase
ANOVA	Analysis of variance
AST	Aspartate aminotransferase
AUC	Area under the concentration-time curve
AUC _{GIR}	Area under the glucose infusion rate-time curve
BG	Blood glucose
BMI	Body mass index
BUN	Blood urea nitrogen
BW	Body weight
CDM	Clinical data management
C.I.	Confidence interval
CL/F	Apparent clearance
CGMS	Continuous glucose monitoring system
C _{max}	Maximum concentration
CRF	Case report form
CRO	Contract Research Organization
CRP	C-reactive protein
CV	Coefficient of variation
DFT	Deviation from target
DMP	Data management plan
DNA	Deoxyribonucleic acid
ECG	Electrocardiogram
eCRF	Electronic CRF
EGP	Endogenous glucose production
FDA	Food and Drug Administration
FFA	Free fatty acid
FPG	Fasting plasma glucose
FSFV	First subject first visit
GCP	Good Clinical Practice
GFR	Glomerular filtration rate
GIR	Glucose infusion rate
GLP-1	Glucagon-like peptide 1
HbA _{1C}	Glycosylated hemoglobin
HBGI	High blood glucose index
HbsAg	Hepatitis B surface antigen
HCV	Hepatitis C virus
HDL	High-density lipoprotein
H-E Clamp	Hyperinsulinemic euglycemic clamp
HIV	Human immunodeficiency virus

HOMA	Homeostasis Model Assessment
HSV	Herpes simplex virus
IB	Investigator's brochure
ICF	Informed consent form
ICH	International Conference on Harmonization
ICU	Intensive care unit
IL	Interleukin
INR	International normalized ratio
IRB	Institutional Review Board
IV	Intravenous
Kg	Kilogram
lb	Pound
LBGI	Low blood glucose index
LDL	Low-density lipoprotein
LS mean	Least square mean
M	Glucose disposal rate during steady state
Mcg	Microgram
MCR	Glucose metabolic clearance rate during steady state
MedDRA	Medical Dictionary for Regulatory Activities
Mg	Milligram
NCA	Non-compartmental analysis
NDA	New Drug Application
Nmol	Nanomol
NPH	Neutral Protamine Hagedorn insulin
NSAID	Non-steroid anti-inflammatory drugs
OAD	Oral antidiabetic drug
OGTT	Oral glucose tolerance test
OTC	Over the counter
PE	Physical examination
PI	Principal Investigator
PK	Pharmacokinetics
PP	Per-Protocol
R _d	Rate of glucose disappearance
rDNA	Recombinant deoxyribonucleic acid
SAP	Statistical analysis plan
SC	Subcutaneous
SI	Insulin Sensitivity Index
SOE	Schedule of events
SUSAR	Suspected unexpected serious adverse reaction
T1DM	Type 1 Diabetes Mellitus
T2DM	Type 2 Diabetes Mellitus
t _½	Terminal insulin half-life

TG	Triglycerides
t_{GIRmax}	Time to maximum glucose infusion rate
T_{max}	Time to maximum serum insulin concentration (in concentration time curve)
TSH	Thyroid-stimulating hormone
U	Unit
UADE	Unanticipated adverse device effect
ULN	Upper limit of normal
US	United States
USP	Unites States Pharmacopeia
VLDL	Very low-density lipoprotein
V_z/F	Apparent volume of distribution at terminal phase
WHO	World Health Organization
YSI	YSI Stat 2300 glucose analyzer

